QUESTIONNAIRE FOR THE CARER (first contact-baseline)

The subject's principal informal carer (NOT CONTRACTED) fills in the questionnaire.

The principal informal carer is the person who is in charge of the patient whose autonomy has been limited for health reasons, and the person who spends more time with him/her or who has a greater responsibility to him/her compared with the other members of the patient's emotional environment.

1. Identification number: _____

2. Carer's date of birth (day/month/year): ____/____/19____

3. Sex:

Female

Male

4. Country: _____

5. Nationality: _____

6. Marital status:

Single Married or cohabiting Divorced Separated

Widow N/A

7. Level of studies completed:

Primary Secondary University None

8. What is your relationship with the subject? Are you his/her...

Sibling Grandchild Son/daughter Nephew/niece Friend

Neighbour Another (please specify) _____ N/A

9. Do you live with the care recipient?

Yes No

10. Since when have you cared for the subject?

 Less than 1 year	 between 4 and 6 years
 between 1 and 2 years	 More than 6 years
 between 2 and 4 years	 NA

HEALTH RELATED PROBLEMS**11. Have you had any health-related problem for caring the subject in the last 12 months?**

YES
 NO → skip to question #13

12. In case of YES, please specify if you suffer any or some of the following problems (multiple choice option):

I am depressed
 I am in treatment because of caregiving
 I am extremely tired
 I have back pain

WORK-RELATED PROBLEM**13. What is your MAIN working situation?**

I am employed
 I am unemployed

- Retired or pensioner ⇒ Skip to question #16
- Domestic tasks ⇒ Skip to question #17
- N/A ⇒ Skip to question #17

14. Have you had any work-related problem for caring the subject in the last 12 months?

- Yes
- No ⇒ Skip to question #16

15. In case of yes, please specify this

- I requested ____ days leave of absence
- I was working ____ hours less a day for ____ days
- I am working ____ hours less a day
- I do not work less hours a day but I have problems fulfilling my working hours
- I had to leave work because of illness the person I care
- Other problems: _____

16. Retirement (only to be answered in case the carer is retired or a pensioner)

a. Have you had to retire early to care for the subject?

- Yes
- No ⇒ Skip to question #17

b. In case of yes, please specify:

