- I retired early at the age of ____ years

SOCIAL, FAMILY AND LEISURE TIME- RELATED PROBLEMS

17. Have you had any family, social o leisure time-related problem for caring the subject in the last 12 months?

- Yes
- No ⇒ Skip to question #19

18. In case of YES, please specify this(multiple choice option):

- I had to reduce my leisure time
- I have conflicts with my partner or my family
- I have no time to see or visit my friends
- I have no time to take care of myself or other people
- I have failed to start a family / I have not been able to have children (or more children)

Regarding the role played by you as PRINCIPAL CARER...

19. How much time do you invest in a normal DAY for each one of the activities?

Please specify the approximate time you spend daily on each activity

On basic hygiene and dressing or changing them	hours	minutes	a day
On bathing or showering them	hours	minutes	a day
On feeding them	hours	minutes	a day
On helping them to move around within the house	hours	minutes	a day

On cooking and preparing meals	hours	minutes	a day
Administration of drugs	hours	minutes	a day

20. How much time do you invest in a normal WEEK on each one of the following activities?

Please specify the approximate time you spend weekly on each activity

On helping them to travel outside the house	hours	minutes	a week
On helping them to contact health care suppliers	hours	minutes	a week
On helping them to organise home adaptations	hours	minutes	a week
On shopping	hours	minutes	a week
On financial, administrative or legal affairs	hours	minutes	a week
On social and leisure activities	hours	minutes	a week
Monitoring and supervision (falls)	hours	minutes	a week

Regarding the role played by OTHER CARERS (e.g. the rest of the family)

21. How much time in a normal DAY do other carers spend on each one of the following activities?

Please specify the approximate time these people spend daily on each activity

On basic hygiene and dressing or changing them	hours	minutes	a day
On bathing or showering them	hours	minutes	a day
On feeding them	hours	minutes	a day

On helping them to move around within the house	hours	minutes	a day
On cooking and preparing meals	hours	minutes	a day
Administration of drugs	hours	minutes	a day

22. How much time do other carers spend in a normal WEEK on each of the following activities?

Please specify the approximate time these people spend weekly on each activity

On helping them to travel outside the house	hours	minutes	a week

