On helping them to contact health care suppliers	hours	minutes	a week
On helping them to organise home adaptations	hours	minutes	a week
On shopping	hours	minutes	a week
On financial, administrative or legal affairs	hours	minutes	a week
On social and leisure activities	hours	minutes	a week
Monitoring and supervision (falls)	hours	minutes	a week

QUESTIONNAIRE FOR THE CARER (week 12)

The subject's principal informal carer (NOT CONTRACTED) fills in the questionnaire

****If it is the first contact that the care has with the study because the person that she/he looks after did not need a carer before or it is a different carer, the carer must fill the baseline's questionnaire.***

1. Identification number_____

HEALTH RELATED PROBLEMS

2. Have you had any health-related problem for caring the subject in the last 3 months?

- YES
- NO → skip to question #4

3. In case of YES, please specify this(multiple choice option)::

- I am depressed
- I am in treatment because of caregiving
- I am extremely tired
- I have back pain

WORK-RELATED PROBLEM

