On social and leisure activities	hours	minutes	a week
Monitoring and supervision (falls)	hours	minutes	a week

Regarding the role played by OTHER CARERS (e.g. the rest of the family)

12. How much time in a normal DAY do other carers spend on each one of the following activities?

Please specify the approximate time these people spend daily on each activity

On basic hygiene and dressing or changing them	hours	minutes	a day
On bathing or showering them	hours	minutes	a day
On feeding them	hours	minutes	a day
On helping them to move around within the house	hours	minutes	a day
On cooking and preparing meals	hours	minutes	a day
Administration of drugs	hours	minutes	a day

13. How much time do other carers spend in a normal WEEK on each of the following activities?

Please specify the approximate time these people spend weekly on each activity

On helping them to travel outside the house	hours	minutes	a week
On helping them to contact health care suppliers	hours	minutes	a week
On helping them to organise home adaptations	hours	minutes	a week
On shopping	hours	minutes	a week
On financial, administrative or legal affairs	hours	minutes	a week
On social and leisure activities	hours	minutes	a week

Monitoring and supervision (falls)	hours	minutes	a week
------------------------------------	-------	-------	-------	---------	--------

QUESTIONNAIRE FOR THE CARER(week 52)

The subject's principal informal carer (NOT CONTRACTED) fills in the questionnaire

****If it is the first contact that the care has with the study because the person that she/he looks after did not need a carer before or it is a different carer, the carer must fill the baseline 's questionnaire.***

1. Identification number_____

HEALTH RELATED PROBLEMS

2. Have you had any health-related problem for caring the subject in the last 6 months?

- YES
- NO → skip to question #4

3. In case of YES, please specify this(multiple choice option)::

- I am depressed
- I am in treatment because of caregiving
- I am extremely tired
- I have back pain
- I have no problem of health because of caregiving

WORK-RELATED PROBLEM

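### At weeks 12 and 52 a new or replacement carer is sent to the baseline form, so problem and leave items cover up to 12 months against 3 or 6 months for continuing carers

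*Combined protocol and SAP*

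**What the plan says.** Annex 3 contains three carer questionnaires: first contact/baseline, week 12 and week 52. The week-12 form covers a carer meeting the study for the first time because the patient "did not need a carer before or it is a different carer, the carer must fill the baseline's questionnaire". The week-52 form repeats the rule: "did not need a carer before or it is a different carer, the carer must fill the baseline 's questionnaire".

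The three forms ask matching questions over different periods. On health, the baseline form (Q11) asks "Have you had any health-related problem for caring the subject in the last 12 months", the week-12 form (Q2) asks "Have you had any health-related problem for caring the subject in the last 3 months" and the week-52 form (Q2) asks "Have you had any health-related problem for caring the subject in the last 6 months". The baseline work question (Q14) is "Have you had any work-related problem for caring the subject in the last 12 months" and the family question (Q17) is "Have you had any family, social o leisure time-related problem for caring the subject in the last 12 months". Their follow-up counterparts use 3 months at week 12 and 6 months at week 52.

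The leave entry ("I requested ____ days leave of absence") and the reduced-hours entries name no period. They follow the work question and so take its window.

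Sections 9.3 and 9.4 say that caregiver burden at 3 and 12 months is collected with the economic questionnaires. Section 10 costs informal care from the time spent helping the patient. Nothing in the documents rescales, flags or separates answers given on different forms.

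**The concern.** Within one visit, the same item would be a 12-month report for some carers and a 3- or 6-month report for others. Carers given the longer window are not a random subset. They become new or different carers after randomisation. Section 4.2 lists the need for a caregiver as an outcome, and Section 3.2 links that need to functional decline. If the intervention changes how often patients need a carer or change carer, it also changes the mix of recall windows in each arm. Carer problems and leave days could then differ between arms for a reason unrelated to burden. At week 12 part of the longer window also falls before randomisation, when the intervention could have had no effect.

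**Working it through.** The plan states no figure on this point, so there is none to reproduce. The check compares the printed windows and then bounds the effect.

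**Step 1. Nominal windows (Annex 3).**

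| Visit | New or different carer (baseline form) | Continuing carer (visit form) | Ratio |
|---|---|---|---|
| Week 12 | 12 months | 3 months | 12/3 = 4.0 |
| Week 52 | 12 months | 6 months | 12/6 = 2.0 |

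**Step 2. Cap by time spent caring.** The items ask about problems caused by caring for this patient, so a new carer's effective window is min(12, t), where t is months of caring.

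| t (months) | Week 12: min(12, t)/3 | Week 52: min(12, t)/6 |
|---|---|---|
| 12 | 4.0 | 2.0 |
| 9 | 3.0 | 1.5 |
| 6 | 2.0 | 1.0 |
| 3 | 1.0 | 0.5 |
| 1 | 0.33 | 0.17 |

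At t = 3 or less (week 12), or t = 6 or less (week 52), the choice of form makes no difference: the carer would report the same t months on either form. A carer who began just after week 12 has about 12 - 3 = 9 months by week 52, hence 1.5-fold. The full 4.0 or 2.0 needs someone already helping for 12 months.

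**Step 3. Reach before randomisation.** Follow-up contacts are 3 and 12 months after discharge (Sections 9.3 and 9.4). A 12-month recall at 3 months reaches 12 - 3 = 9 months before discharge, and so before randomisation. At 12 months it reaches 12 - 12 = 0, about the date of discharge, which is after randomisation.

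**Step 4. Effect on mean leave days with no true difference.** Let a and b be the shares of new or changed carers in the two arms, and k the mean window ratio for those carers. At a constant rate of leave,

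ratio = ((1 - a) + k·a) / ((1 - b) + k·b).

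The documents give no shares. The values of a and b below are assumptions.

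| Case | k | a = 10%, b = 5% | a = 20%, b = 10% |
|---|---|---|---|
| Week 12, all have the 4-fold window | 4 | 1.30/1.15 = 1.13 | 1.60/1.30 = 1.23 |
| Week 12, half 4-fold and half 1-fold | 2.5 | 1.15/1.075 = 1.07 | 1.30/1.15 = 1.13 |
| Week 52, all have the 2-fold window | 2 | 1.10/1.05 = 1.05 | 1.20/1.10 = 1.09 |
| Week 52, all have the 1.5-fold window | 1.5 | 1.05/1.025 = 1.02 | 1.10/1.05 = 1.05 |

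**Step 5. Yes/no problem items.** With an assumed risk p per 3 months and independent new onsets, 12-month risk is 1 - (1 - p)^4: 5% becomes 18.5%, 10% becomes 34.4% and 20% becomes 59%. These are upper figures. Many response options describe current states (depression, tiredness, back pain), and a persistent problem gives much the same answer over 3 or 12 months.

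**Step 6. Can it be repaired afterwards?** Baseline Q10 is the only duration item. Its shortest category is anything under one year, with no start date. Two carers with 1 and 11 months of caring look identical, so their answers cannot be put on a common window.

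**The case against.** The strongest reply is that no specified analysis is harmed. Section 4.2 defines caregiver burden by the Zarit scale and Section 9.1 by the Modified Caregiver Strain Scale. Neither is built from these items. Section 10 values time spent on care, asked on all three forms for a normal day or week, and does not cost leave days. No score or arm comparison is defined for the problem or leave items. This largely stands and is why the priority is low. It is not a full answer, because Sections 9.3 and 9.4 name the economic questionnaires as the source for caregiver burden at follow-up.

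A second reply is that the forms do not say the baseline questionnaire replaces the visit form. If both were completed, answers on the visit's window would exist. That is possible, though replacement is the more natural reading, and sites could differ.

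A third reply is that the effect fails for one of the two triggers. Where the patient had no carer at baseline, a carer seen at week 12 can have cared for at most about 3 months plus the hospital stay, so the ratio is near 1 or below. This stands. A reader might infer that the arm with more new carers always gets longer windows, but the documents do not support that: the excess arises only for carers whose caring time exceeds the visit's window.

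**Conclusion.** The concern holds in a limited form. The routing rule gives non-comparable recall windows in a group formed after randomisation, and the data collected do not allow a later correction.

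The excess is at most 4-fold at week 12 and 2-fold at week 52, chiefly for a replacement carer who was already helping. It is at most about 1.5-fold at week 52 for a carer who began just after week 12, and absent for a recent starter. In arm-level mean leave days this is at most 1.13 to 1.23 at week 12 (1.07 to 1.13 if only half have the 4-fold window) and 1.02 to 1.09 at week 52. These figures rest on assumed carer shares, a constant rate of leave, and replacement of the visit form.

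Two stronger readings are not supported. One is that the informal-care cost is biased; the costed time items have no recall window. The other is that pre-randomisation time contaminates both visits; it can enter materially only at week 12. The effect is confined to the health, work, leave and family-problem items.

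**What to change.** Reword the instruction on the week-12 and week-52 forms so that a new or different carer completes only the descriptive baseline items (Q2-Q10) plus the date caring began, and then completes that visit's own form with its own recall window. The nominal window ratio becomes 1.0 at both visits, and the start date shows how much of the window each carer could have experienced.

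The cost is one sentence on each form, one date field and a change in eCRF routing, with no extra contact.

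This makes carers comparable within a visit. It does not close a separate gap: the contacts are 12 - 3 = 9 months apart and the week-52 form looks back 6, so about months 3 to 6 after discharge stay uncovered for everyone.

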4. WHAT IS YOUR MAIN WORKING SITUATION?

- I am employed

- I am unemployed
- Retired or pensioner ⇒ Skip to question #7
- Domestic tasks ⇒ Skip to question #8
- N/A ⇒ Skip to question #8

5. Have you had any work-related problem for caring the subject in the last 3 months?

- Yes
- No ⇒ Skip to question #8

6. In case of yes, please specify this

- I requested ___ days leave of absence
- I was working ___ hours less a day for ___ days
- I am working ___ hours less a day
- I do not work less hours a day but I have problems fulfilling my working hours
- I had to leave work because of illness the person I care
- Other problems: _____

7. Retirement (only to be answered in case the carer is retired or a pensioner)

c. Have you had to retire early to care for the subject?

- Yes
- No ⇒ Skip to question #8

d. In case of yes, please specify:

- I retired early at the age of ___ years

SOCIAL, FAMILY AND LEISURE TIME- RELATED PROBLEMS

8. Have you had any family, social o leisure time-related problem for caring the subject in the last 3 months?

Yes No ⇒ Skip to question #10

9. In case of YES, please specify this(multiple choice option)::

- I had to reduce my leisure time
- I have conflicts with my partner or my family
- I have no time to see or visit my friends
- I have no time to take care of myself or other people
- I have failed to start a family / I have not been able to have children (or more children)

Regarding the role played by you as PRINCIPAL CARER...

10. How much time do you invest in a normal DAY for each one of the activities?

Please specify the approximate time you spend daily on each activity

On basic hygiene and dressing or changing them	hours	minutes	a day
On bathing or showering them	hours	minutes	a day
On feeding them	hours	minutes	a day
On helping them to move around within the house	hours	minutes	a day
On cooking and preparing meals	hours	minutes	a day

Administration of drugs	hours	minutes	a day
-------------------------	-------	-------	-------	---------	-------

11. How much time do you invest in a normal WEEK on each one of the following activities?

Please specify the approximate time you spend weekly on each activity

On helping them to travel outside the house	hours	minutes	a week
On helping them to contact health care suppliers	hours	minutes	a week
On helping them to organise home adaptations	hours	minutes	a week
On shopping	hours	minutes	a week
On financial, administrative or legal affairs	hours	minutes	a week
On social and leisure activities	hours	minutes	a week
Monitoring and supervision (falls)	hours	minutes	a week

Regarding the role played by OTHER CARERS (e.g. the rest of the family)

12. How much time in a normal DAY do other carers spend on each one of the following activities?

Please specify the approximate time these people spend daily on each activity

On basic hygiene and dressing or changing them	hours	minutes	a day
On bathing or showering them	hours	minutes	a day
On feeding them	hours	minutes	a day
On helping them to move around within the house	hours	minutes	a day
On cooking and preparing meals	hours	minutes	a day
Administration of drugs	hours	minutes	a day

13. How much time do other carers spend in a normal WEEK on each of the following activities?

Please specify the approximate time these people spend weekly on each activity

On helping them to travel outside the house	hours	minutes	a week
On helping them to contact health care suppliers	hours	minutes	a week
On helping them to organise home adaptations	hours	minutes	a week
On shopping	hours	minutes	a week
On financial, administrative or legal affairs	hours	minutes	a week
On social and leisure activities	hours	minutes	a week

Monitoring and supervision (falls)	hours	minutes	a week
------------------------------------	-------	-------	-------	---------	--------

QUESTIONNAIRE FOR THE CARER(week 52)

The subject's principal informal carer (NOT CONTRACTED) fills in the questionnaire

****If it is the first contact that the care has with the study because the person that she/he looks after did not need a carer before or it is a different carer, the carer must fill the baseline 's questionnaire.***

1. Identification number_____

HEALTH RELATED PROBLEMS

2. Have you had any health-related problem for caring the subject in the last 6 months?

- YES
- NO → skip to question #4

3. In case of YES, please specify this(multiple choice option)::

- I am depressed
- I am in treatment because of caregiving
- I am extremely tired
- I have back pain
- I have no problem of health because of caregiving

WORK-RELATED PROBLEM

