Informal care includes different types of unpaid support which serve to compensate for the inability of subjects, usually provided by relatives or friends. This information is obtained from questionnaires applied directly to caregivers in which time spent on helping the elderly in basic Activities of Daily Living and Instrumental Activities will be specified. The time spent on these activities will be evaluated in monetary terms using 'proxy goodmethod "or" replacement method "which assesses the time spent on informal care adjusted to market prices of a professional who has to do this work (social service Careful formal).

The economic evaluation will be developed to take into account several aspects: financing health care (including only direct health costs), finance formal care (including the direct costs of health and social services) and social perspective (including all relevant costs: direct medical care + formal care (social services) and informal care.

Outcome measures:

Cost-effectiveness analysis

The cost-effectiveness analysis (CEA) is the most common test used in health economics to decide between different treatments for the same condition. In a CEA, the costs are measured in monetary units, while the benefits are measured as outcomes or in natural units. "Incremental cost-effectiveness ratio" (ICER) is estimated to show a difference in health outcomes per unit cost, after a follow-up period between intervention and usual care. The incremental cost-effectiveness is expressed by the following relation:

$$ICER = \frac{C_a - C_b}{B_a - B_b}$$

Where Ca is the cost of the intervention group and Cb is the cost of the usual care group. Ba will be health benefits in the intervention group and Bb health benefits in the usual care group, both measured in terms of change of the clinical results of the baseline.

In this study the primary outcomes will be the difference in functional status after the intervention compared with usual care group. This study will assess the cost-effectiveness of the intervention of a geriatrician compared with usual care from the perspective of society and the health care system.

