b. **In the case of yes, who is your principal carer?**

- Family member ⇒ Fill in the carer questionnaire and skip to question #6
- Another non-contracted person (friend) ⇒ Fill in the carer questionnaire and skip to question #6
- Professional carer (contracted or provided by an entity)

c. **If you use the services of a professional carer,**

How many hours a week? _____ hours a week

Who pays for the service and how much?

- I pay the entire cost of _____ € per hour

(Alternative, if the subject does not know the cost per hour)

- I pay the entire cost of _____ € per month
- The cost is covered by social security or another entity
- The cost is partially covered by social security or another entity, I pay _____ € per hour

(Alternative, if the subject does not know the cost per hour)

- The cost is partially covered by social security or another entity, I pay _____ € per month

6. Hospitalisation

Have you been admitted to hospital in the last 12 months?

- Yes
- No

7. Health and social services you have required and days of service received by according to economic system during the last month and the last 6 months.

Mark the services you have required, number of days received and form of payment. In case you have required a service and have not received it, note the reason number (see the possible reasons below the table).

Kinds of services	You have needed to receive..	Days service received according to economic system			Reason for which they have not received the service (*)
		Free of charge	Direct payment	Mixed (public and private)	
During the last month...		During the last month...			
1. Telecare		— days	— days	— days	

2. Domiciliary care /help		— days	— days	— days	
3. Day centre		— days	— days	— days	
4. Occupational centre or centre for cultural, recreational and leisure activities		— days	— days	— days	
5. Other:		— days	— days	— days	
In the last 6 months...		In the last 6 months...			
6. Respite services: Temporary stays		— days	— days	— days	
7. Residential centres		— days	— days	— days	
8. Other:		— days	— days	— days	

(*) Reasons: 1 – Waiting list. 2 – Not available in the setting. 3 – Cannot pay it. 4 – Does not comply with any of the requirements. 5 – Other reasons.

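### The carer forms ask six care tasks as time on a normal day without asking on how many days a week help is given, so informal care hours are ambiguous for help that is not daily

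*Combined protocol and SAP*

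**What the plan says.** In the carer questionnaires of Annex 3, question 10 at weeks 12 and 52 (question 19 at baseline) asks the principal carer "How much time do you invest in a normal DAY for each one of the activities", with the instruction "Please specify the approximate time you spend daily on each activity". Six rows follow: personal hygiene and dressing, bathing ("On bathing or showering them"), feeding, moving about indoors, cooking, and giving medicines. Each is answered in hours and minutes a day. Question 12 (question 21 at baseline) repeats the six rows for the rest of the family and other helpers: "How much time in a normal DAY do other carers spend on each one of the following activities".

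Seven further activities are asked by the week: "How much time do you invest in a normal WEEK on each one of the following activities". In the baseline subject questionnaire, paid care is also asked by the week ("How many hours a week"), and social services are counted in days received.

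Section 10, under informal care, states the use of the answers: "The time spent on these activities will be evaluated in monetary terms". The method is replacement cost, which prices carer time at what a professional would charge. Section 10 does not say how a daily figure becomes weekly or period hours, or that a normal day means an average over the week.

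**The concern.** A figure per day gives weekly hours only if the number of days is known or the respondent has already averaged. The forms secure neither. They also expect help that is not daily: the baseline form asks "Do you live with the care recipient", and separate questions cover other carers, who need not come every day. Bathing need not be daily even for a carer who lives with the patient.

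The quantity at stake is informal care time, which enters the societal perspective in section 10. Cost-effectiveness from society's perspective is a listed secondary objective (section 3.2). An intervention meant to improve independence could plausibly change how often help is needed rather than how long each occasion takes, and frequency is what these six rows do not record. Once a form is completed, nothing else on it shows which reading the carer used.

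**Working it through.** The plan gives no figure for this quantity, so there is none to reproduce. The check compares the hours given with the hours that would be computed from the form.

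**Inputs.** From the documents: the unit (hours and minutes a day), the six rows, the absence of a day count, and pricing of the time. Assumed for illustration: 45 minutes of bathing per helping day, on d days a week. Multiplying by 7 is the natural conversion, but the plan does not state it.

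**Formulas.** With m minutes per helping day:
- true weekly hours = m × d / 60
- computed weekly hours = recorded minutes a day × 7 / 60

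**One carer, m = 45, d = 2.** True: 45 × 2 / 60 = 1.5 h/week.

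| Reading of the question | Recorded (min/day) | Computed (h/week) |
|---|---|---|
| A day on which help is given | 45 | 45 × 7 / 60 = 5.25 |
| A typical day, which has no bath | 0 | 0 |
| Average over the week | 90 / 7 = 12.9 | 1.5 |

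**Size by frequency.** Under the helping-day reading the overstatement is 7/d, whatever m is:

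| d | 1 | 2 | 3 | 4 | 5 | 6 | 7 |
|---|---|---|---|---|---|---|---|
| 7/d | 7.0 | 3.5 | 2.33 | 1.75 | 1.4 | 1.17 | 1.0 |

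At d = 7 all three readings agree and there is no error.

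**A change in helping days, 5 to 2, m = 45.** True: 3.75 to 1.5, a change of −2.25 h/week.
- Helping-day reading: 5.25 both times, change 0. The saving is lost.
- Typical-day reading: 5.25 (help on most days) to 0 (no help on most days), change −5.25. The saving is exaggerated 5.25 / 2.25 = 2.33 times.
- Averaging: −2.25, correct.

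**Direction in a mixture.** Let shares a, b and c of carers use the three readings in that order, with a + b + c = 1. The mean recorded change is −(5.25b + 2.25c). It equals −2.25 when 5.25b = 2.25(a + b), that is when b = 0.75a. With fewer typical-day answers than that, the saving is understated; with more, it is overstated. The documents give no information on a, b or c.

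The exaggeration arises only when the fall crosses from most days to few days. For a fall from 7 to 5 days the true change is 5.25 to 3.75 = −1.5 h/week, while the helping-day and typical-day readings both record 0.

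**The case against.** **The question can be read sensibly.** It asks for approximate daily time, and a carer who averages gives a usable answer. This stands. A reader might infer that the answers cannot be turned into hours at all, or that every carer who does not help daily is misrecorded. The documents support neither: averaged answers and daily care convert correctly. What remains is that the form does not ask for an average, so the analyst cannot separate the readings.

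**The daily/weekly split is reasoned.** Feeding, dressing, moving indoors, cooking and medicines usually recur every day where help is needed, while shopping, travel and finances do not. The principal carer is defined as the person with the most time or the greatest responsibility, so is less likely to be an occasional helper. This stands too, and it confines the problem mainly to bathing and to carers who do not come daily, above all other carers.

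**The bias need not hide a saving.** A reader might infer that the informal care saving is attenuated. If a share s of carers gave helping-day figures, the rest averaged, and minutes per occasion were equal in both arms, a difference in days would indeed be shown at (1 − s) of its size. That leaves out the typical-day reading, which can exaggerate the change. Attenuation is not established.

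**Follow-up is by telephone** (sections 9.3 and 9.4), so a caller could clarify the question. Possible, but no such script or instruction is given.

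**Materiality is limited.** Informal care enters one of three costing perspectives. This stands and bears on the priority of the point. The probit models planned for formal and informal care do not remove the need for hours, because the societal ICER still requires a cost per arm.

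**Conclusion.** The point holds as a measurement ambiguity in six rows of each carer form, for tasks or carers that are not daily. For such help, informal care hours can be misstated and made noisier, with bias of uncertain direction: a fall in helping days may not show, or may be exaggerated. In the worked example the computed figure is 5.25, 0 or 1.5 h/week against a true 1.5. The helping-day reading overstates hours by 1.17 to 7 times for 6 down to 1 helping days.

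These sizes rest on assumed minutes and days and on multiplying by 7. How many carers are affected, and which reading they would use, is unknown from the documents, so no effect on the trial's ICER can be computed. The reach is the informal care hours and the societal costs and ICER built on them. The clinical outcomes, the QALYs, the sample size and the two narrower costing perspectives (health care; health care plus social services) are untouched. It is a cheap improvement, worth making because the error cannot be corrected after collection.

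**What to change.** Add a days-a-week box to each of the six rows, for the principal carer and for other carers, on the baseline, week 12 and week 52 forms. Word the time column as time on a day when help is given. State in section 10 that weekly hours = time per helping day × days per week, and compute informal care cost from these hours.

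For bathing alone, an alternative is to move the row to the weekly question, as the forms already do for seven activities. Moving all six is more debatable, because carers would have to add up daily tasks over seven days. A bare instruction to average over the week is lighter still, but the analyst could not check that it was followed.

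The cost is one short box per row: 6 rows × 2 questions = 12 boxes a form. It also breaks comparability with any forms already completed. For those, run a sensitivity analysis over the possible readings, for example by scaling non-zero answers by d/7 over d = 1 to 7 for other carers and for carers who do not live with the patient. Recorded zeros that may hide occasional help can be covered only by assumption.
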